5.2 Safety Endpoints

5.2.1 Primary Safety Endpoint

Not applicable.

5.2.2 Secondary Safety Endpoint

 Incidence of treatment emergent adverse events (TEAEs) related to treatment with diluted Radiesse, as reported by the treating investigator throughout the study.

5.3 Other Subject Data

Other variables of interest are:

- Subject disposition (including number of subjects enrolled, number of subjects with retreatment, number of discontinuations and reason for discontinuations)
- Incidence and nature of protocol deviations
- - Previous and concomitant medication
 - Previous and concomitant non-drug treatment and procedures
 - Medical history and concomitant diseases

CCI

6 Statistical Analysis Methods

Adequate descriptive statistics will be provided for each endpoint, by treatment group and overall, where appropriate. Metric descriptive statistics will comprise number of observations, mean, standard deviation, quartiles, minimum, median, and maximum. Frequency tables for qualitative endpoints/variables will display absolute and percent frequencies (n, %) per category where the denominator will be chosen according to the adequate analysis population. Ordered categorical data will be summarized by metric descriptive statistics and frequency tables, where appropriate. All variables will be analyzed as absolute data and as change from baseline assessment, as applicable. Summaries by categorical variables/groups should always include a 'Total' category. Mean, quartiles and median will be reported to one decimal place more than the data were collected, for the standard deviation two decimal places more will be displayed. For derived data, an adequate number of decimal places will be chosen. Frequency tables will include the number of missing values. Percentages will be calculated using the denominator of all subjects in a specified population or treatment group. The denominator will be specified in a footnote to the tables for clarification if necessary. Percentages will be reported to one decimal place.

Descriptive confidence limits and descriptive p-values will be given, where appropriate. If not otherwise specified, statistical tests will be conducted two-sided at type I error rate 5% and CIs

will be two-sided with confidence level 95%. All data captured in the eCRF and all image analysis data will be listed. For (sub-) groups with five or less subjects, no statistical test will be performed and confidence intervals will not be displayed due to the low number of subjects.

P-values will be reported to four decimal places. P-values below 0.0001 will be presented as '<0.0001'.

In the sections below, the term baseline severity refers to the severity of wrinkles on the MAS Décolleté Wrinkles-At Rest as assessed by a blinded live rater.

6.1 Effectiveness Endpoints

Table 1 gives an overview on the effectiveness endpoints and their corresponding analysis population.

6.1.1 Primary Effectiveness Endpoint

The primary effectiveness endpoint is the proportion of responders (responder rate) at Week 24, defined as subjects with at least 1-point improvement on MAS "Décolleté Wrinkles-At Rest" from baseline, as assessed live by the blinded evaluator. For baseline, the scores assessed at Screening will be used for both treatment groups.

The primary effectiveness endpoint will be analyzed based on the ITT population. The responder rate at Week 24 will be summarized as counts and percentages for the treatment and control groups.

6.1.1.1 Primary analysis

The first hypothesis of the primary analysis is to demonstrate that the response rate Π_A at Week 24 is statistically significantly larger than 50% in treated subjects, i.e.,

 H_{10} : $\Pi_A \le 50 \%$ versus H_{11} : $\Pi_A > 50 \%$.

[figure not shown]
This 50% threshold is commonly used in aesthetic medical device studies to measure a meaningful response.

The second hypothesis is to show statistical superiority of treatment over untreated control. Superiority of treatment means that the response rate in the 'Treatment' group, Π_A , is statistically significantly larger than the response rate in the 'Control/Delayed treatment' group, Π_B , i.e.

 H_{20} : $\Pi_A \leq \Pi_B$ versus H_{21} : $\Pi_A > \Pi_B$.

Both hypotheses will be tested using the lower limits of the 95% CIs (two-sided), based on Wilson scores. The lower limit of the 95% Wilson CI must exceed the margin of 50% responder rate to reject the first Null hypothesis H_{10} . The lower limit of the 95% Newcombe CI for the difference between the responder rates in the 'Treatment' group and the 'Control/Delayed treatment' group $(\Pi_A - \Pi_B)$ must be greater than zero to reject the second Null hypothesis (H_{20}) .

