9 STUDY POPULATION AND RESTRICTIONS

9.1 Number of Subjects and Sites

Approximately 152 subjects will be randomized at up to ten study sites in the US. approximately 120 evaluable subjects are planned for this study.

All enrolled subjects will participate for a maximum duration of 84 weeks (\pm 14 days). All subjects will sign and date the ICF before randomization and before any study-related procedures are undertaken.

In general, discontinued subjects will not be replaced. In case of more than 10% missing primary effectiveness data due to a public health emergency (e.g. COVID-19), additional subjects can be randomized.

Additional information regarding subject enrollment and randomization is provided within the sample size justification in Section 13.1.

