13.1 Estimation of Sample Size

The primary effectiveness analysis considers the proportion of subjects with at least 1-point (≥ 1-point) improvement on the MAS Décolleté Wrinkles-At Rest scale at Week 24 compared to baseline as assessed live by a blinded evaluator. Subjects will be randomized into two treatment groups as detailed in Section 13.2.

approximately 152 subjects, 114 subjects in the treatment Group A and 38 subjects in the untreated-control/delayed-treatment Group B, will be randomized for this study. Regarding the safety evaluation, in a sample size of 152 subjects an adverse event with a true incidence of 1.5% will be observed at least once with a probability of 89.9%.

Sample size calculations were performed using nQuery software (Version 8.5, Statistical Solutions Ltd., 2019).

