13.2 Randomization

All eligible subjects will be randomized 3:1 to one of the following groups:

- Group A: Treatment with diluted Radiesse at Day 1, Week 6, and Week 12.
- Group B: Untreated control followed by delayed treatment with diluted Radiesse at Week 24 (after primary endpoint assessment), Week 30, and Week 36.

The randomization will be block-stratified by study site as described in Section 10.3.

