13.4.1 Effectiveness Analyses

13.4.1.1 Primary Effectiveness Endpoint

The primary effectiveness endpoint (Section 7.2.1.1) will be summarized as counts and percentages for the treatment and control groups.

Two hypothesis tests will be performed, based on the primary effectiveness endpoint. These tests will be evaluated in a sequential order on the ITT. To control for multiplicity, a hierarchical-testing procedure will be performed at a one-sided α level of 0.025.

The first hypothesis of the primary analysis is to demonstrate that the response rate is statistically significantly larger than 50% in treated subjects. This 50% threshold is commonly used in aesthetic medical device studies to measure a meaningful response.

The second hypothesis is to show statistical superiority of treatment over untreated control. Both hypotheses will be tested using the lower limits of the 95% CIs (two-sided), based on Wilson scores. The lower limit of the 95% Wilson CI must exceed the margin of 50% responder rate to reject Hypothesis 1 (H_{10}). The lower limit of the 95% Newcombe CI must be greater than zero to reject Hypothesis 2 (H_{20}).

13.4.1.1.1

[figure not shown]

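### The visible superiority test compares crude responder rates although the screening MAS At Rest grade is available in both arms; standardising over it is a modest, low-cost gain and does not correct an invalid test.

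*SAP*

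**What the plan says.** Protocol 13.4.1.1 sets two ordered tests on the primary endpoint: "a hierarchical-testing procedure will be performed at a one-sided α level of 0.025". The first (H1) is a single-arm test: "The lower limit of the 95% Wilson CI must exceed the margin of 50% responder rate to reject the first Null hypothesis". The second (H2) is the comparison with control. Under SAP 6.1.1.1, "The lower limit of the 95% Newcombe CI for the difference between the responder rates in the" two groups must lie above zero. Neither document attaches a covariate, stratum or model to that rule.

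SAP 6.1.1 takes the screening score as baseline in both groups. Just before SAP 6.1, the plan fixes a definition: "the term baseline severity refers to the severity of wrinkles on the MAS" At Rest scale, graded live by a blinded rater. In the visible text this variable only breaks down the GAIS results (SAP 6.1.2), and at Week 24 only for the treated group.

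On balance between arms, Protocol 13.2 says: "The randomization will be block-stratified by study site as described in Section 10.3". No other stratum is visible. The planned arm sizes are "114 subjects in the treatment Group A and 38 subjects in the" control group (Protocol 13.1). MAS-Dynamic is to be compared in the same way as the primary endpoint (Protocol 13.4.1.2, SAP 6.1.2).

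**The concern.** Response is defined as a change from the screening grade, and the study targets wrinkles from moderate to severe, so the starting grade is a natural candidate for a prognostic variable. Balance on it is left to chance, and the smaller arm has only 38 subjects. A crude difference carries any chance imbalance in a prognostic variable into the estimate. A difference standardised to one severity mix does not.

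H2 is the test that carries the stated effectiveness objective. If the arms turn out visibly different in baseline severity, readers will ask whether the estimate reflects treatment or starting grade. An adjustment chosen after the data are seen is open to challenge, whereas one fixed beforehand is not. The baseline value is already collected.

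**Working it through.** **Inputs from the documents.** 114 and 38 subjects (Protocol 13.1); 3:1 allocation (Protocol 13.2); about 120 evaluable (Protocol 9.1), which is 90 and 30 if 3:1 holds; one-sided level 0.025 (Protocol 13.4.1.1).

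**Assumptions.** The documents do not show response rates, the share of severe subjects or the effect of grade. I take two grades, half the subjects severe, a gap g in response between grades of 0 to 30 points (the same in both arms), 65% response in treated subjects, and 20% or 40% in controls.

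**The plan's own figures.** 152 × 0.75 = 114 and 152 × 0.25 = 38. The probability of at least one event of 1.5% incidence is 1 - 0.985^152 = 0.8995, which agrees with the stated 89.9%. The power behind 152 cannot be reproduced, because its inputs are withheld.

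**Chance imbalance.** The SD of the between-arm difference in the share of severe subjects is sqrt[p(1-p)(1/114 + 1/38)].
- p = 0.5: 0.0937; 1.96 × 0.0937 = 0.184, or ±18.4 points.
- p = 0.3: 0.0858; ±16.8 points.
- p = 0.5 with 90 and 30: 0.1054; ±20.7 points.

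**Shift in the crude difference at the edge of that range.** Imbalance × g, at 114/38 and p = 0.5: 0.184 × 0.10 = 1.8 points, 0.184 × 0.20 = 3.7 points, 0.184 × 0.30 = 5.5 points. At 90/30 the figures are 2.1, 4.1 and 6.2.

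**Variance of the difference.** The crude variance is pA(1-pA)/114 + pB(1-pB)/38. With two equal grades, standardising removes g²/4 from each p(1-p). Example at 65% versus 20%, g = 20 points:
- crude: 0.2275/114 + 0.16/38 = 0.00621;
- standardised: 0.2175/114 + 0.15/38 = 0.00586, a ratio of 0.943.

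Estimating the strata costs about 1.5% in samples of this size, which gives about 0.957. Simulation (100,000 trials per scenario, weights equal to the observed severity mix, Wald tests) gives the ratio of adjusted to crude variance at 114/38:

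| Gap g | 65% vs 20% | 65% vs 40% |
|---|---|---|
| 0 | 1.015 | 1.016 |
| 10 points | 1.001 | 1.006 |
| 20 points | 0.957 | 0.972 |
| 30 points | 0.885 | 0.920 |

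**Effect on H2 power at 114/38.** At 65% versus 20%, power is 99.9% crude and 99.9 to 100.0% adjusted. At 65% versus 40% it is about 78% crude, and 78, 78, 79 and 82% adjusted for gaps of 0, 10, 20 and 30 points.

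**Which test is tighter.** Under the stated rules H1 needs at least 68/114 responders (59.6%). At that minimum, H2 still passes with up to 15/38 control responders (39.5%). At a 65% treated rate, H1 power is 90.2%. H2 power is 100.0, 99.9, 97.3 and 78.2% for control rates of 10, 20, 30 and 40%, by exact enumeration.

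**Validity of the crude rule.** The exact one-sided type I error of the Newcombe rule at 114/38 is 1.4, 1.9, 2.3 and 2.7% for common rates of 10, 20, 30 and 50%.

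**The case against.** A reader might infer that the crude comparison is biased or has an inflated error rate. The documents do not support that. Under randomization, imbalance in grade is random error that the interval already covers, and the exact error of 1.4 to 2.7% lies close to or below the nominal 2.5%.

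A reader might also infer that precision is certainly being lost. That depends on a gap between grades for which the documents give no figure. With a gap of 0 to 10 points, adjustment gains nothing or costs slightly. The mechanism is plausible but not shown: a moderate subject can also improve by one grade, so neither the direction nor the size of the effect can be read from the plan. The larger gaps are not always possible either. At a 10% control rate, two equal strata cannot differ by 30 points. The 3.7-point shift combines a 95%-extreme imbalance with an assumed gap. For scale, the crude 95% half-width at 65% versus 20% is 1.96 × 0.0789, about 15 points.

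A third tempting reading is that the plan contains no severity adjustment at all. That cannot be said. Protocol 13.4.1.1.1 and the text on missing data and subgroups are withheld, and so is the imputation model. A severity-adjusted sensitivity analysis may exist, and the imputation model may contain baseline grade.

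All of this stands, and it limits the size of the point. It does not change the visible deciding rule, which is complete as written and unadjusted. It also does not make adjustment harmful, since the worst case found at the planned arm sizes is a variance increase of about 2%.

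**Conclusion.** The point holds as a modest improvement to the deciding H2 analysis. A baseline grade that is already collected and probably prognostic is left out of the visible comparison. Using it would protect the estimate from a chance imbalance that could plausibly reach 18 points, and would reduce variance by 3 to 4% at a 20-point gap or 8 to 11% at a 30-point gap. The effect on the trial's decision is negligible when untreated response is low. It matters only if that response is near 40%, where power rises from about 78% to 79% or 82% with gaps of 20 or 30 points. H1 is a single-arm test and is unaffected.

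These sizes rest on assumed response rates, two equally common grades and the same gap in both arms. They come from weights equal to the observed severity mix with Wald tests, so a stratified Newcombe interval would differ slightly.

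**What to change.** Before any Week 24 comparison is seen, amend SAP 6.1.1.1 and Protocol 13.4.1.1 together, since changing the SAP alone would set the two documents against each other on the primary test. The new text should:

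- take the H2 lower limit from one named estimator of the risk difference standardised over baseline MAS At Rest grade, for example the stratified Newcombe interval with Mantel-Haenszel weights;
- state how that limit is pooled across the imputed data sets;
- state how sparse strata are handled, because at an assumed 30% severe the severe control stratum would hold about 0.30 × 38 = 11 subjects (9 of 30 evaluable), and say whether the SAP 6 rule that suppresses intervals in groups of five or fewer applies to strata;
- keep the crude Newcombe interval as supportive;
- do the same for MAS-Dynamic, with the baseline Dynamic grade.

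The target remains a difference in responder rates, so the zero margin, the alpha level, the test order and H1 do not change. The SAP's opening section allows amendment before the final analysis. That may be too late, because SAP 6.4.2 has the interim analysis produce the tables planned for the final one.

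The cost is a protocol amendment with the ethics approval that Protocol 14.6 requires, SAP wording, minor coding, and a variance increase of at most about 2% if grade proves not to be prognostic. No new data are needed. If the withheld text already specifies a severity-adjusted sensitivity analysis, the change mainly consists of giving that analysis the deciding role.

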6.1.2 Secondary Effectiveness Endpoints

MAS Décolleté Wrinkles-Dynamic response

[figure not shown]
Treatment comparisons for the secondary effectiveness endpoint proportion of responders at Week 24 on MAS Décolleté Wrinkles Dynamic as assessed live by a blinded evaluator will be conducted analogous to the primary effectiveness endpoint. Descriptive two-sided 95% Wilson score-based

```
CIs, CCI will be performed CCI descriptive summary statistics. CCI
```

The Global Aesthetic Improvement Scale

The iGAIS and sGAIS assessments describing the overall impression of post-treatment aesthetic change specific to the décolleté compared to baseline photograph as well as percentage of subjects with improvement in iGAIS and sGAIS will be evaluated at Week 24 by baseline severity and in total for the 'Treatment' group.

For each GAIS category (i.e., -3 = very much worse, -2 = much worse, -1 = worse, 0 = no change, +1 = improved, +2 = much improved, +3 = very much improved), counts (n) and percentages (%) will be presented.

The Global Aesthetic Improvement Scale

[figure not shown]
The iGAIS and sGAIS assessments describing the overall impression of post-treatment aesthetic change specific to the décolleté compared to baseline photograph as well as percentage of subjects with improvement will be evaluated for each post-treatment follow-up visit (except Week 24) and by baseline severity and in total. For subjects receiving an optional retreatment at Week 36 in 'Treatment' group, an additional summary will be used to report iGAIS and sGAIS scores relative to the Week 36 reference photograph.

For each GAIS category (i.e., -3 = very much worse, -2 = much worse, -1 = worse, 0 = no change, +1 = improved, +2 = much improved, +3 = very much improved), counts (n) and percentages (%) will be presented by treatment group.

Additionally, iGAIS and sGAIS will be categorized in classes of "improvement" (scores +1 to +3) and "no improvement" (scores -3 to 0) and frequencies for these categories will be provided. Descriptive two-sided 95% Wilson CIs will be calculated for subjects with "improvement".

Moreover, metric descriptive summary statistics will be provided for the iGAIS and sGAIS by treatment group.

6.2 Safety Analyses

All safety analyses will be performed on the SES, if not specified otherwise.

For interim and final analysis adverse events (AEs) will be coded according to the Medical Dictionary for Regulatory Activities (MedDRA) version in effect at the time the respective database is closed.

Treatment-emergent AEs (TEAEs) are defined as AEs with onset or worsening at or after the first administration of study treatment. In this regard, an AE with onset prior to treatment that worsens at or after first administration of study treatment must be documented as a new TEAE with onset at the time of worsening.

Only TEAEs will be summarized CCI using MedDRA preferred terms (PTs) within the system organ classes (SOCs).

[figure not shown]

[figure not shown]
6.2.1 Primary Safety Endpoint

Not applicable.

6.2.2 Secondary Safety Endpoints

Incidences of TEAEs related to the treatment with diluted Radiesse will be summarized by treatment group and total, overall and by treatment period by PT and SOC.

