8 CLINICAL INVESTIGATION PLAN

8.1 Overview of Study Design

will be eligible for enrollment.

CCI

The treating investigators that will participate in the study are board-certified dermatologists and/or plastic surgeons.

All eligible subjects will be randomized at a 3:1 ratio to treatment with diluted Radiesse (Group A) or to untreated control followed by delayed treatment with diluted Radiesse (Group B).

Subjects will be followed for up to Week 84 CCI

Subjects in Group A will receive three treatments in total at Day 1, Week 6, and Week 12. Additionally, subjects in Group A will have the option for one additional retreatment at Week 36.

Subjects in Group B will receive three treatments upon completion of all effectiveness assessments at Week 24.

Untreated-control/delayed-treatment subjects will not be offered an additional optional retreatment.

Subjects will have a screening period of up to 10 days. All enrolled subjects will participate in the study for a maximum duration of 84 weeks (± 14 days).

The primary effectiveness endpoint, the proportion of responders on MAS Décolleté Wrinkles-At Rest, will be assessed live by a blinded evaluator at Week 24 and compared to baseline. Response is defined as at least 1-point improvement from baseline. Standard safety parameters will be monitored throughout the study.

CCI

provides an overview of the visit schedule and the study design. details a Schedule of Events for each visit.

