8.2 Discussion of Study Design, Including the Choice of Control Groups

As detailed in Section 8.1, this is a prospective, multicenter, randomized, evaluator-blinded, parallel-group study. The study will be conducted at up to ten sites in the US. This multicenter design approach will increase the representativeness of the study results and decrease site-related biases. Randomization will eliminate selection bias in treatment assignment.

Since no approved, marketed products are currently available in the United States (US) for treatment of the décolleté region, an untreated-control group will be used for this study. To maximize the number of subjects exposed to acquire adequate safety data, control subjects will receive a delayed treatment with diluted Radiesse upon completion of all Week 24 effectiveness assessments.

The study duration of 84 weeks (i.e., main period and safety follow-up period) represents a reasonable timeframe to assess effectiveness as well as delayed-onset and/or long-term AEs.[14, 17, 33] A sequence of three treatment sessions at intervals of 6 weeks was chosen based on the pilot study and on the assumption that significant increases of collagen Type I and III are demonstrated at 4 to 9 months after treatment with diluted Radiesse. Published results suggest a cycle in which the highest deposition of new collagen and elastin occurs around 4 months after injection, with stability achieved by 9 months.[10, 23, 29, 35-37] Therefore, treatment intervals of 6 weeks were chosen, and an observation of 12 weeks after the last injection (24 weeks following initial injection), which corresponds with the effectiveness follow-up established by the consensus guideline.[24] Subjects randomized to treatment at Day 1 will also be eligible for optional retreatment at Week 36 to achieve further aesthetic décolleté enhancement.

Dilution ratio and volumes to be administered in this study (see Sections 10.5.1.2 and 10.5.1.5) represent a safe standard for décolleté treatment based on the consensus guidelines for the injection of diluted Radiesse for skin tightening. [24] As recommended by the consensus guideline for the majority of individuals and as supported by the pilot study, 1.5 mL CaHA diluted 1:2 with physiologic saline solution was chosen as an average indicated volume and dilution.

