10.5.2 Selection and Timing of Treatment for Each Subject

For subjects randomized to the treatment group (Group A), treatment will occur at Day 1, Week 6, and Week 12. Subjects in Group A may receive an optional retreatment at Week 36 to achieve optimal cosmetic results, at the discretion of the treating investigator and the subject.

For subjects randomized to the delayed-treatment group (Group B), treatment will occur at Weeks 24, 30 and 36.

In the event of a public health emergency, further treatments may be halted or postponed.

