11 STUDY PROCEDURES

11.1 Visit Schedule

The investigation activities and visit schedule are detailed in the Schedule of Events

The purpose of the screening visit (Visit 1) is to determine subject eligibility for participation in this study and must be completed -10 to -3 days prior to Day 1 (Visit 2). Eligible subjects will be randomized at the screening visit.

Subjects randomized to Group A will receive treatment at Day 1, Week 6, and Week 12. Group A subjects also have the option for one additional retreatment at Week 36. Subjects randomized to Group B will remain untreated until Week 24, when the primary effectiveness endpoint will be evaluated. Upon completion of all primary effectiveness assessments, Group B subjects will be treated (i.e., will receive delayed treatment) at Weeks 24, 30, and 36. Group B subjects will not be offered an additional retreatment.

All treatments should be administered at the study site by the treating investigator, occurring only after completion of all required pre-injection procedures and assessments.

Safety follow-up will occur until Week 84 ± 14 days.

The primary endpoint visit will occur at Week 24 (± 7 days)

In the case of premature discontinuation of the study, a final assessment (End of main period visit) should be performed.

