13.4.2.1 Secondary Safety Endpoints

Incidences of TEAEs related to the treatment with diluted Radiesse will be summarized by treatment group and total, overall and by study period by PT and SOC.

13.4.2.2 ^{CCI}

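### The overall related-TEAE incidence pools a nominal 84 weeks after first injection in Group A with 60 in Group B, so for late-onset events Group B, and through it the total, is lower by design

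*SAP*

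**What the plan says.** SAP 5.2.2 defines the secondary safety endpoint as the incidence of TEAEs related to diluted Radiesse, "as reported by the treating investigator throughout the study". SAP 6.2.2 says the incidences "will be summarized by treatment group and total, overall and by treatment period by PT and SOC". Protocol 13.4.2.1 has them "summarized by treatment group and total, overall and by study period by PT and SOC", so the two documents name the period split differently.

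Under SAP 6.2 and Protocol 13.4.2 an event becomes treatment-emergent only from the first administration of study treatment. The analysis set is everyone treated at least once (SAP 4).

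The schedule is as follows:

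- **Group A:** "Subjects in Group A will receive three treatments in total at Day 1, Week 6, and Week 12" (Protocol 8.1). In addition, "Subjects in Group A may receive an optional retreatment at Week 36" (Protocol 10.5.2).
- **Group B:** "treatment will occur at Weeks 24, 30 and 36" (Protocol 10.5.2).
- **End of observation, both groups:** "Safety follow-up will occur until Week 84 ± 14 days" (Protocol 11.1).

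Protocol 8.2 states that the 84-week study duration "represents a reasonable timeframe to assess effectiveness as well as delayed-onset and/or long-term AEs". It also explains that controls receive delayed treatment to enlarge the safety database.

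**The concern.** The end of observation is fixed on the study calendar, while the start of risk is fixed by each subject's first injection. The two groups start 24 weeks apart and stop together. A crude incidence to Week 84 therefore gives the groups different lengths of observation, and the total column is a mixture of the two.

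This does not matter for reactions that appear soon after injection. It matters for delayed-onset and long-term events, which Protocol 8.2 gives as a reason for the long follow-up. For those events the two columns can differ when the underlying risk is the same. The total is then neither an 84-week nor a 60-week risk. The safety objective concerns repeat treatment, and every Week 36 injection, including every optional retreatment, has only a nominal 48 weeks of observation behind it.

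**Working it through.** **Inputs.** Planned group sizes are 114 and 38, total 152 (Protocol 13.1). Injection weeks are 0, 6, 12 and optionally 36 in Group A, and 24, 30, 36 in Group B (Protocol 10.5.2). Observation ends at Week 84 ± 14 days (Protocol 11.1). The arithmetic assumes that all randomized subjects are treated and complete follow-up. Neither the timing of late events nor the uptake of retreatment is given in the documents.

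**1. The plan's own safety figure.** The chance of at least one event with true incidence 1.5% in 152 subjects is 1 − 0.985^152 = 0.89947, which reproduces the stated 89.9%. The plan does not say over what period the 1.5% applies.

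**2. Nominal follow-up.**

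| | After first injection | After last injection |
|---|---|---|
| Group A, not retreated | 84 − 0 = 84 weeks | 84 − 12 = 72 weeks |
| Group A, retreated | 84 − 0 = 84 weeks | 84 − 36 = 48 weeks |
| Group B | 84 − 24 = 60 weeks | 84 − 36 = 48 weeks |

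Group B has 60/84 = 71.4% of Group A's time after first injection. Person-weeks are 114 × 84 + 38 × 60 = 9,576 + 2,280 = 11,856, a mean of 11,856/152 = 78.0 weeks. That is 92.9% of the 152 × 84 = 12,768 that 84 weeks for everyone would give.

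**3. Size under a constant hazard (assumption).** Let p be the 84-week incidence. Group B shows 1 − (1 − p)^(60/84), and the total is (114 × p + 38 × Group B)/152.

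| p (= Group A) | Group B | Total | Total relative to p |
|---|---|---|---|
| 1.5% | 1.07% | 1.39% | 0.929 |
| 5% | 3.60% | 4.65% | 0.930 |
| 10% | 7.25% | 9.31% | 0.931 |

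Group B is about 28% lower and the total about 7% lower. At p = 10% the A:B ratio is 10/7.25 = 1.38 with identical underlying risk. If the 1.5% is an 84-week incidence, the chance of seeing at least one event is 1 − 0.985^114 × (1 − 0.01074)^38 = 88.2%, against 89.9%.

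**4. Range without the constant-hazard assumption.** Let f be the share of 84-week events with onset later than 60 weeks after first injection. Group B then shows p(1 − f), and the total is p(1 − 0.25f), because 38/152 = 0.25. With p = 1.5%:

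| f | Group B | Total | Total lower by | Chance of at least one event |
|---|---|---|---|---|
| 0 | 1.50% | 1.50% | 0% | 89.9% |
| 20% | 1.20% | 1.43% | 5% | 88.7% |
| 50% | 0.75% | 1.31% | 12.5% | 86.6% |
| 100% | 0% | 1.13% | 25% | 82.1% |

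Group A stays at 1.50% in every row. On a common 60-week clock both groups show p(1 − f), so the artefact disappears.

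**5. What the common windows can deliver.** A final visit at Week 82 gives Group B 82 − 24 = 58 weeks after first injection and 82 − 36 = 46 weeks after the last. The 60 and 48 weeks are therefore nominal, and censoring is needed. A 60-week window from first injection also leaves a retreated Group A subject only 60 − 36 = 24 weeks after the Week 36 injection. Non-retreated Group A subjects and Group B have 60 − 12 = 48 weeks after their third. A second clock, from the last injection, is needed to describe repeat treatment.

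**The case against.** The strongest reply has four parts.

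- **Redaction.** Protocol 13.4.2.2 is blacked out, and text is missing from Protocol 13.4.2 and SAP 6.2. Definitions of the periods, a common window or a time-to-onset analysis may stand there. This is right, and the fix is conditional on it. The mismatch between *study period* and *treatment period* is visible either way.
- **The period split.** The planned table is already broken down by period, which may separate the windows. It may, but no definition is visible. A split on the study calendar would keep the 24-week offset, whereas one counted from each subject's injections could remove it.
- **No inference is affected.** The visible text plans no between-group test of TEAEs, and each group's figure is a correct incidence over its own follow-up. This stands: a reader might infer a biased safety test or a type I error problem, and the documents support neither. What remains is how a descriptive table will be read.
- **Size.** With the plan's 1.5% and a constant hazard, Group B loses 38 × (1.50% − 1.07%) = 0.16 of a subject. Even at an assumed 10% it loses 38 × 2.75% = about one. With no onsets after 60 weeks, nothing is lost. Protocol 6.3 also reports that common injection reactions generally resolved within seven days. This limits the point to late-onset events but does not remove it.

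Protocol 8.2 also calls the study duration reasonable; it does not promise every subject 84 weeks after injection. The point is that the follow-up actually delivered should be stated, not that a commitment is broken.

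**Conclusion.** The point holds for late-onset events. The overall incidence puts 84 weeks after first injection in Group A beside 60 in Group B, and 72 weeks after last injection beside 48. The visible text offers no common clock. Group B's incidence is lower by design for onsets beyond about 60 weeks after first injection, and the total is lower only through Group B. Under a constant hazard this is about 28% for Group B and 7% for the total; across all possible late-onset shares the total falls by 0% to 25%.

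A reader might infer that all the reported rates are understated. The schedule does not support that. Group A has its full nominal 84 weeks, events within 60 weeks are captured in both groups apart from dropout, and early injection-site reactions are untouched.

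The sizes rest on the planned 114 and 38 subjects and complete follow-up. Control subjects who leave before Week 24 never enter the safety set, which would shrink Group B's weight in the total. This is a modest problem of interpretation that is cheap to correct.

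**What to change.** Keep the planned table. Unless the redacted text already provides it, add to SAP 6.2.2 related-TEAE incidence by group and total, timed from each subject's own injections and censored at last contact:

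1. Cumulative incidence to a nominal 60 weeks after first injection.
2. For events with onset on or after the last injection, cumulative incidence to a nominal 48 weeks after it, with Group A shown by retreatment status.

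Exposure-adjusted rates per subject-year are an acceptable alternative, with the caveat that they compare cleanly only if the rate is roughly constant over time.

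Footnote the overall total with its mixed follow-up. Use one term and one definition for the period split in SAP 6.2.2 and Protocol 13.4.2.1. In Protocol 8.2 state the nominal follow-up delivered: 84 weeks after first injection in Group A only, 60 in Group B, and 48 after any Week 36 injection.

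No visit, treatment or sample size changes. Onset dates (Protocol 12.1.2) and injection dates (Protocol 10.9) are already recorded, and the SAP's opening section allows amendment before the final analysis. The cost is a few extra tables and a slightly less favourable statement of long-term follow-up.
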